Table 49: ITT Analysis of Ordinal Clinical Outcome - ITT Analysis Population

Timepoint	Ordinal Clinical Outcome	Azithromycin (N=X)		Placebo (N=X)	
		n	% (95% CI) ¹	n	% (95% CI) ^a
D5V	1	xx	xx (xx, xx)	xx	xx (xx, xx)
	2	xx	xx (xx, xx)	xx	xx (xx, xx)
	3	xx	xx (xx, xx)	xx	xx (xx, xx)
	4	xx	xx (xx, xx)	xx	xx (xx, xx)
	5	xx	xx (xx, xx)	xx	xx (xx, xx)
	6	xx	xx (xx, xx)	xx	xx (xx, xx)
	7	xx	xx (xx, xx)	xx	xx (xx, xx)
	8	xx	xx (xx, xx)	xx	xx (xx, xx)
	Missing	xx	xx (xx, xx)	xx	xx (xx, xx)
D11V	1	xx	xx (xx, xx)	xx	xx (xx, xx)
	2	xx	xx (xx, xx)	xx	xx (xx, xx)
	3	xx	xx (xx, xx)	xx	xx (xx, xx)
	4	xx	xx (xx, xx)	xx	xx (xx, xx)
	5	xx	xx (xx, xx)	xx	xx (xx, xx)
	6	xx	xx (xx, xx)	xx	xx (xx, xx)
	7	xx	xx (xx, xx)	xx	xx (xx, xx)
	8	xx	xx (xx, xx)	xx	xx (xx, xx)
	Missing	xx	xx (xx, xx)	xx	xx (xx, xx)
D28V	1	xx	xx (xx, xx)	xx	xx (xx, xx)
	2	xx	xx (xx, xx)	xx	xx (xx, xx)
	3	xx	xx (xx, xx)	xx	xx (xx, xx)
	4	xx	xx (xx, xx)	xx	xx (xx, xx)
	5	xx	xx (xx, xx)	xx	xx (xx, xx)
	6	xx	xx (xx, xx)	xx	xx (xx, xx)
	7	xx	xx (xx, xx)	xx	xx (xx, xx)
	8	xx	xx (xx, xx)	xx	xx (xx, xx)
	Missing	xx	xx (xx, xx)	xx	xx (xx, xx)

N = Number of subjects in the ITT Population in the given treatment group.

^a95% CI estimated using the Wilson Method.

Table 50: Analysis of Ordinal Clinical Outcome at D5V - ATP-5 Analysis Population

[Implementation note: The Missing row will be deleted if no subject in the ATP-5 analysis population had missing OCO.]

Ordinal Clinical Outcome	Azithromycin (N=X)		Placebo (N=X)	
	n	% (95% CI) ^a	n	% (95% CI) ^a
1	xx	xx (xx, xx)	xx	xx (xx, xx)
2	xx	xx (xx, xx)	xx	xx (xx, xx)
3	xx	xx (xx, xx)	xx	xx (xx, xx)
4	xx	xx (xx, xx)	xx	xx (xx, xx)
5	xx	xx (xx, xx)	xx	xx (xx, xx)
6	xx	xx (xx, xx)	xx	xx (xx, xx)
7	xx	xx (xx, xx)	xx	xx (xx, xx)
8	xx	xx (xx, xx)	xx	xx (xx, xx)
Missing	xx	xx (xx, xx)	xx	xx (xx, xx)

N = Number of subjects in the ATP-5 Population in the given treatment group.
^a95% CI estimated using the Wilson Method.

Table with similar format:

Table 51: Analysis of Ordinal Clinical Outcome at D11V - ATP-11 Analysis Population

[Implementation note: The Missing row will be deleted if no subject in the ATP-11 analysis population had missing OCO.]

Table 52: Number of Times Clinical Improvement was Achieved - ITT Analysis Population

Number of Times	Azithromycin (N=X)		Placebo (N=X)	
	n	% (95% CI) ^a	n	% (95% CI) ^a
0	xx	xx (xx, xx)	xx	xx (xx, xx)
1	xx	xx (xx, xx)	xx	xx (xx, xx)
2	xx	xx (xx, xx)	xx	xx (xx, xx)
3	xx	xx (xx, xx)	xx	xx (xx, xx)
Missing ^b	xx	xx (xx, xx)	xx	xx (xx, xx)

N = Number of subjects in the ITT Population in the given treatment group.

^a95% CI estimated using the Wilson Method.

^bNumber of subjects missing clinical improvement at all three timepoints (D5V, D11V, D28V) will be classified as missing.

Table 53: ITT Analysis of DOOR Based on Number of Times Clinical Improvement was Achieved Across D5V, D11V, and D28V - ITT Analysis Population with Complete Data

Tie-Breaking	Statistic	Value
No tie-breaking	Subjects with non-missing DOOR– n (%)	x (x)
	Pr(Higher DOOR in Placebo Arm) ^a (95% CI) ^b	x.xx (x.xx, x.xx)
	P-value ^c	x.xxx
Duration of antibiotic use as tie-breaker	Subjects with non-missing DOOR– n (%)	x (x)
	Pr(Higher DOOR in Placebo Arm) ^a (95% CI) ^b	x.xx (x.xx, x.xx)
	P-value ^c	x.xxx

Note: DOOR was calculated based on subjects with non-missing clinical improvement for at least one of the timepoints.
^aProbability of Higher DOOR in Placebo Arm + 0.5 Probability of Equal DOOR. CI obtained through inversion of the F-test used to compute the p-value.
^bObtained through using inversion of the Mann-Whitney U test with a normal approximation and assuming the null hypothesis distribution variance provided in Section 8.2.8 correcting for ties.
^cP-value obtained by Mann-Whitney U Test. P-value boundary of 0.05 is used to conclude statistical significance.

Table 54: ITT Analysis of DOOR Based on Average Ordinal Clinical Outcome from Study Day 1 Through Study Day 11 - ITT Analysis Population with Complete Data

Statistic	Value
Subjects with non-missing DOOR– n (%)	x (x)
Pr(Higher DOOR in Placebo Arm) ^a (95% CI) ^b	x.xx (x.xx, x.xx)
P-value ^c	x.xxx

Note: DOOR was calculated based on subjects with non-missing OCO at atleast one of the timepoints. Missing values were ignored when calculating average OCO.
 
^aProbability of Higher DOOR in Placebo Arm + 0.5 Probability of Equal DOOR. CI obtained through inversion of the F-test used to compute the p-value.
 
^bObtained through using inversion of the Mann-Whitney U test with a normal approximation and assuming the null hypothesis distribution variance provided in Section 8.2.8 correcting for ties.
 
^cP-value obtained by Mann-Whitney U Test. P-value boundary of 0.05 is used to conclude statistical significance.
	

Table 55: ITT Analysis of DOOR Based on Average Ordinal Clinical Outcome from D5V, D11V, and D28V - ITT Analysis Population with Complete Data

Statistic	Value
Subjects with non-missing DOOR– n (%)	x (x)
Pr(Higher DOOR in Placebo Arm) ^a (95% CI) ^b	x.xx (x.xx, x.xx)
P-value ^c	x.xxx

Note: DOOR was calculated based on subjects with non-missing OCO at atleast one of the timepoints. Missing values were ignored when calculating average OCO.
 
^aProbability of Higher DOOR in Placebo Arm + 0.5 Probability of Equal DOOR. CI obtained through inversion of the F-test used to compute the p-value.
 
^bObtained through using inversion of the Mann-Whitney U test with a normal approximation and assuming the null hypothesis distribution variance provided in Section 8.2.8 correcting for ties.
 
^cP-value obtained by Mann-Whitney U Test. P-value boundary of 0.05 is used to conclude statistical significance.
	

Table 56: Risk of Mild, Moderate, or Severe Solicited Events from Study Day 1 to D5V - ATP-5 Analysis Population

Symptom	Azithromycin (N=X)		Placebo (N=X)		Risk Difference (95% CI) ^b	P-Value ^c
	n (%)	95% CI ^a	n (%)	95% CI ^a		
Any Symptom	x (x)	(x, x)	x (x)	(x, x)	x.x (x.x, x.x)	x.xxx
Abdominal Pain	x (x)	(x, x)	x (x)	(x, x)	x.x (x.x, x.x)	x.xxx
Vomiting	x (x)	(x, x)	x (x)	(x, x)	x.x (x.x, x.x)	x.xxx
Diarrhea	x (x)	(x, x)	x (x)	(x, x)	x.x (x.x, x.x)	x.xxx
Allergic Reaction	x (x)	(x, x)	x (x)	(x, x)	x.x (x.x, x.x)	x.xxx
Candidiasis	x (x)	(x, x)	x (x)	(x, x)	x.x (x.x, x.x)	x.xxx

N = Number of subjects in the ATP-5 analysis population and the respective treatment group with complete records from study Day 1 to D5V.
^a95% CI for proportions calculated using the Wilson method.
^b95% CI for the difference in proportions, placebo relative to azithromycin, calculated using the Miettinen–Nurminen method.
^cP-values obtained by Fisher’s Exact Test.

Table 57: Risk of Moderate or Severe Solicited Events from Study Day 1 to D5V - ATP-5 Analysis Population

Symptom	Azithromycin (N=X)		Placebo (N=X)		Risk Difference (95% CI) ^b	P-Value ^c
	n (%)	95% CI ^a	n (%)	95% CI ^a		
Any Symptom	x (x)	(x, x)	x (x)	(x, x)	x.x (x.x, x.x)	x.xxx
Abdominal Pain	x (x)	(x, x)	x (x)	(x, x)	x.x (x.x, x.x)	x.xxx
Vomiting	x (x)	(x, x)	x (x)	(x, x)	x.x (x.x, x.x)	x.xxx
Diarrhea	x (x)	(x, x)	x (x)	(x, x)	x.x (x.x, x.x)	x.xxx
Allergic Reaction	x (x)	(x, x)	x (x)	(x, x)	x.x (x.x, x.x)	x.xxx
Candidiasis	x (x)	(x, x)	x (x)	(x, x)	x.x (x.x, x.x)	x.xxx

N = Number of subjects in the ATP-5 analysis population and the respective treatment group with complete records from Study Day 1 to D5V.
^a95% CI for proportions calculated using the Wilson method.
^b95% CI for the difference in proportions, placebo relative to azithromycin, calculated using the Miettinen–Nurminen method.
^cP-values obtained by Fisher's Exact Test.

Table 58: Risk of Severe Solicited Events from Study Day 1 to D5V - ATP-5 Analysis Population

Symptom	Azithromycin (N=X)		Placebo (N=X)		Risk Difference (95% CI) ^b	P-Value ^c
	n (%)	95% CI ^a	n (%)	95% CI ^a		
Any Symptom	x (x)	(x, x)	x (x)	(x, x)	x.x (x.x, x.x)	x.xxx
Abdominal Pain	x (x)	(x, x)	x (x)	(x, x)	x.x (x.x, x.x)	x.xxx
Vomiting	x (x)	(x, x)	x (x)	(x, x)	x.x (x.x, x.x)	x.xxx
Diarrhea	x (x)	(x, x)	x (x)	(x, x)	x.x (x.x, x.x)	x.xxx
Allergic Reaction	x (x)	(x, x)	x (x)	(x, x)	x.x (x.x, x.x)	x.xxx
Candidiasis	x (x)	(x, x)	x (x)	(x, x)	x.x (x.x, x.x)	x.xxx

N = Number of subjects in the ATP-5 analysis population and the respective treatment group with complete records from Study Day 1 to D5V.
^a95% CI for proportions calculated using the Wilson method.
^b95% CI for the difference in proportions, placebo relative to azithromycin, calculated using the Miettinen–Nurminen method.
^cP-values obtained by Fisher's Exact Test.

Table 59: Risk of Mild, Moderate, or Severe Solicited Events from Study Day 1 to Day 11 - ATP-11 Analysis Population

Symptom	Azithromycin (N=X)		Placebo (N=X)		Risk Difference (95% CI) ^b	P-Value ^c
	n (%)	95% CI ^a	n (%)	95% CI ^a		
Any Symptom	x (x)	(x, x)	x (x)	(x, x)	x.x (x.x, x.x)	x.xxx
Abdominal Pain	x (x)	(x, x)	x (x)	(x, x)	x.x (x.x, x.x)	x.xxx
Vomiting	x (x)	(x, x)	x (x)	(x, x)	x.x (x.x, x.x)	x.xxx
Diarrhea	x (x)	(x, x)	x (x)	(x, x)	x.x (x.x, x.x)	x.xxx
Allergic Reaction	x (x)	(x, x)	x (x)	(x, x)	x.x (x.x, x.x)	x.xxx
Candidiasis	x (x)	(x, x)	x (x)	(x, x)	x.x (x.x, x.x)	x.xxx

N = Number of subjects in the ATP-11 analysis population and the respective treatment group with complete records from Study Day 1 to Day 11.
^a95% CI for proportions calculated using the Wilson method.
^b95% CI for the difference in proportions, placebo relative to azithromycin, calculated using the Miettinen–Nurminen method.
^cP-values obtained by Fisher's Exact Test.

Table 60: Risk of Moderate or Severe Solicited Events from Study Day 1 to Day 11 - ATP-11 Analysis Population

Symptom	Azithromycin (N=X)		Placebo (N=X)		Risk Difference (95% CI) ^b	P-Value ^c
	n (%)	95% CI ^a	n (%)	95% CI ^a	n (%)	95% CI ^a
Any Symptom	x (x)	(x, x)	x (x)	(x, x)	x.x (x.x, x.x)	x.xxx
Abdominal Pain	x (x)	(x, x)	x (x)	(x, x)	x.x (x.x, x.x)	x.xxx
Vomiting	x (x)	(x, x)	x (x)	(x, x)	x.x (x.x, x.x)	x.xxx
Diarrhea	x (x)	(x, x)	x (x)	(x, x)	x.x (x.x, x.x)	x.xxx
Allergic Reaction	x (x)	(x, x)	x (x)	(x, x)	x.x (x.x, x.x)	x.xxx
Candidiasis	x (x)	(x, x)	x (x)	(x, x)	x.x (x.x, x.x)	x.xxx

N = Number of subjects in the ATP-11 analysis population and the respective treatment group with complete records from Study Day 1 to Day 11.
^a95% CI for proportions calculated using the Wilson method.
^b95% CI for the difference in proportions, placebo relative to azithromycin, calculated using the Miettinen–Nurminen method.
^cP-values obtained by Fisher’s Exact Test.

Table 61: Risk of Severe Solicited Events from Study Day 1 to Day 11 - ATP-11 Analysis Population

Symptom	Azithromycin (N=X)		Placebo (N=X)		Risk Difference (95% CI) ^b	P-Value ^c
	n (%)	95% CI ^a	n (%)	95% CI ^a	n (%)	95% CI ^a
Any Symptom	x (x)	(x, x)	x (x)	(x, x)	x.x (x.x, x.x)	x.xxx
Abdominal Pain	x (x)	(x, x)	x (x)	(x, x)	x.x (x.x, x.x)	x.xxx
Vomiting	x (x)	(x, x)	x (x)	(x, x)	x.x (x.x, x.x)	x.xxx
Diarrhea	x (x)	(x, x)	x (x)	(x, x)	x.x (x.x, x.x)	x.xxx
Allergic Reaction	x (x)	(x, x)	x (x)	(x, x)	x.x (x.x, x.x)	x.xxx
Candidiasis	x (x)	(x, x)	x (x)	(x, x)	x.x (x.x, x.x)	x.xxx

N = Number of subjects in the ATP-11 analysis population and the respective treatment group with complete records from Study Day 1 to Day 11.

^a95% CI for proportions calculated using the Wilson method.

^b95% CI for the difference in proportions, placebo relative to azithromycin, calculated using the Miettinen–Nurminen method.

^cP-values obtained by Fisher’s Exact Test.

Table 62: Analysis of Mean Changes in PCT Levels - ATP-5 Analysis Population

Clinical Status	Time Point	Statistic	Azithromycin (N=X)	Placebo (N=X)	Difference in Mean PCT Changes, Placebo Relative to Azithromycin (95% CI) ^b	P-value ^c
Clinical Improvement	Baseline	n	x	x	--	--
		Mean (SD)	x.x (x.x)	x.x (x.x)	--	--
		Median	x.x (x.x)	x.x (x.x)	--	--
		Range (Min, Max)	x.x (x.x)	x.x (x.x)	--	--
	D5V	n	x	x	--	--
		Mean (SD)	x.x (x.x)	x.x (x.x)	--	--
		Median	x.x (x.x)	x.x (x.x)	--	--
		Range (Min, Max)	x.x (x.x)	x.x (x.x)	--	--
		Mean PCT Changes from Baseline (95% CI) ^a	x.x (x.x, x.x)	x.x (x.x, x.x)	x.x (x.x, x.x)	x.xxx
	Clinical Failure	Baseline	n	x	x	--
		Mean (SD)	x.x (x.x)	x.x (x.x)	--	--
		Median	x.x (x.x)	x.x (x.x)	--	--
		Range (Min, Max)	x.x (x.x)	x.x (x.x)	--	--
		Mean PCT Changes from Baseline (95% CI) ^a	x.x (x.x, x.x)	x.x (x.x, x.x)	x.x (x.x, x.x)	x.xxx
	All Subjects	Baseline	n	x	x	--
		Mean (SD)	x.x (x.x)	x.x (x.x)	--	--
		Median	x.x (x.x)	x.x (x.x)	--	--
		Range (Min, Max)	x.x (x.x)	x.x (x.x)	--	--

Table 62: Analysis of Mean Changes in PCT Levels - ATP-5 Analysis Population (Continued)

Clinical Status	Time Point	Statistic	Azithromycin (N=X)	Placebo (N=X)	Difference in Mean PCT Changes, Placebo Relative to Azithromycin (95% CI) ^b	P-value ^c
	D5V	n	x	x	--	--
		Mean (SD)	x.x (x.x)	x.x (x.x)	--	--
		Median	x.x (x.x)	x.x (x.x)	--	--
		Range (Min, Max)	x.x (x.x)	x.x (x.x)	--	--
		Mean PCT Changes from Baseline (95% CI) ^a	x.x (x.x, x.x)	x.x (x.x, x.x)	x.x (x.x, x.x)	x.xxx

N = Number of subjects in the ATP-5 population in the corresponding treatment group. n = Number of subjects in the ATP-5 population with data at the corresponding time point, clinical status, and treatment group.
 All PCT values reported as '< x.xx' were imputed to '0.5*x.xx' for analysis.
^a95% CI for the mean PCT changes from baseline calculated using the 2.5th and 97.5th percentiles of PCT changes from baseline using Bootstrap.
^b95% CI for the difference in mean PCT changes calculated using the 2.5th and 97.5th percentiles of the difference in mean PCT changes using Bootstrap.
^cP-value obtained by Wilcoxon Test.

Table 63: Logistic Regression Model to Evaluate the Relationship of Change in Mean PCT Levels at D5V with Clinical Improvement Adjusting for Treatment Group - ATP-5 Analysis Population

Model Parameter	Parameter Category	Parameter Estimate	Standard Errors	Odds Ratio (95% CI)	P-value
Intercept	NA	x.x	x.xx	-	x.xxx
Change in Mean PCT from Baseline	NA	x.x	x.xx	x.x (x.xx, x.xx)	x.xxx
Treatment Group	Azithromycin	-	-	-	-
	Placebo	x.x	x.xx	x.x (x.xx, x.xx)	x.xxx
Centered Study Day of D5V	NA	x.x	x.xx	x.x (x.xx, x.xx)	x.xxx

N = Number of subjects in the ATP-5 population.
The parameter estimate for change in mean PCT from baseline is interpreted as the expected change in log odds of clinical improvement for a one-unit increase in change in Mean PCT from baseline given study day of D5V is 5.

Table 64: Logistic Regression Model to Evaluate the Relationship of PCT Level at Screening with Detection of a Viral or Bacterial Pathogen

Pathogen Type	Model Parameter	Parameter Category	Parameter Estimate	Standard Errors	Odds Ratio (95% CI)	P-value
Viral	Intercept	NA	x.x	x.xx	-	x.xxx
	PCT Level at Screening	NA	x.x	x.xx	x.x (x.xx, x.xx)	x.xxx
Bacterial	Intercept	NA	x.x	x.xx	-	x.xxx
	PCT Level at Screening	NA	x.x	x.xx	x.x (x.xx, x.xx)	x.xxx

Note: This analysis included all subjects, randomized and non-randomized, with non-missing PCT level at screening and non-missing pathogen detection data.

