**Secondary:**

1. To compare groups receiving azithromycin versus placebo with regard to all antibiotic use by Days 11 and 28.
2. To compare groups receiving azithromycin versus placebo with regard to return visits to a physician's office or urgent care by Days 11 and 28.
3. To compare groups receiving azithromycin versus placebo with regard to emergency department visits by Days 11 and 28.
4. To compare groups receiving azithromycin versus placebo with regard to hospitalization by Days 11 and 28 if not hospitalized at the enrollment and randomization visit.
5. To compare groups receiving azithromycin versus placebo with regard to improvement in presenting symptoms by Days 11 and 28.
6. To compare the efficacy of azithromycin versus placebo on Day 11 in subjects with suspect LRTI and PCT levels of  $\leq 0.25$  ng/mL at enrollment using a non-inferiority approach.
7. To compare the efficacy of azithromycin versus placebo on Day 28 in subjects with suspect LRTI and PCT levels of  $\leq 0.25$  ng/mL at enrollment using a non-inferiority approach.
8. To compare the efficacy of azithromycin versus placebo in subjects with suspected LRTI and PCT levels of  $\leq 0.25$  ng/mL at Day 5 using a superiority approach, employing the "Response Adjusted for Days of Antibiotic Risk (RADAR)" methodology.
9. To compare groups receiving azithromycin versus placebo in regard to solicited events by Day 5.
10. To compare groups receiving azithromycin versus placebo in regard to hospitalization or visits to an ED, outpatient clinic, or urgent care center for worsening or persistent LRTI after randomization by Day 5.

11. To compare groups receiving azithromycin versus placebo in regard to improvement in vital sign abnormalities or symptoms present at enrollment, on Day 5.
12. To compare groups receiving azithromycin versus placebo in regard to new vital sign abnormalities or symptoms on Day 5, or deterioration in symptoms relative to the enrollment visit on Day 5.

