8.2.12. Deterioration in LRTI Symptoms at D5V Using ATP-5 Analysis Population

A forest plot of 95% CIs for the risk difference of deterioration in any qualifying symptom (cough, sputum production, chest pain, or difficulty breathing) at D5V compared to baseline will be analyzed in subjects having the symptom at baseline will be provided in [Figure 12](#) using ATP-5 Analysis Population. Results will also be reported in [Table 39](#), and tests for differences in proportions between treatment arms will be given by Fisher's exact tests. Since Fisher's test cannot be inverted, there is no corresponding CI. Therefore, the Miettinen–Nurminen method will be used to compute all 95% CIs for risk differences. Note that the CI results might not be consistent with the p-value from Fisher's exact test.

8.2.13. New occurrence of Vital Sign Abnormality or Fever at D5V Using ATP-5 Analysis Population

Using ATP-5, a forest plot of 95% CIs for the risk difference of new vital sign abnormality at D5V compared to baseline or fever in the 24 hours preceding or at D5V will be provided in [Figure 14](#). Results will also be reported in [Table 42](#) to include a p-value from Fisher's exact test. Since Fisher's test cannot be inverted, there is no corresponding CI. Therefore, the Miettinen–Nurminen method will be used to compute all 95% CIs for risk differences. Note that the CI results might not be consistent with the p-value from Fisher's exact test.

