8.3.7. Deterioration in LRTI Symptoms at D11V Using ATP-11 Analysis Population

A forest plot of 95% CIs for the risk difference for placebo compared to azithromycin of deterioration in any qualifying symptom and in each symptom individually (cough, sputum production, chest pain, or difficulty breathing) at D5V compared to baseline will be analyzed in subjects having the symptom at baseline will be provided in [Figure 13](#) using ATP-5 Analysis Population. Results will also be reported in [Table 40](#), and tests for differences in proportions between treatment arms will be given by Fisher's exact tests. The Miettinen–Nurminen method will be used to compute all 95% CIs for risk differences.

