
Table with similar format:

Table 36: Improvement in LRTI Symptoms or Fever at D28V - ATP-28 Analysis Population

[Implementation Note: Update the footnote to use ATP-28.]

Table 37: ITT Analysis of DOOR at Day 5 - ITT Analysis Population

Statistic	Value
Subjects with all DOOR components measured – n (%)	x (x)
Subjects with one or more DOOR components imputed – n (%)	x (x)
Pr(Higher DOOR in Placebo Arm) ^a (95% CI) ^a	x.xx (x.xx, x.xx)
P-value ^b	x.xxx

^aProbability of Higher DOOR in Placebo Arm at D11V + 0.5 Probability of Equal DOOR. 95% CI obtained through inversion of the F-test used to compute the p-value.
 
^bP-value obtained by Mann-Whitney U Test. P-value boundary of 0.05 is used to conclude statistical significance. It is important to note that conclusions from DOOR analyses must rely on a detailed assessment of the DOOR components as well as consideration of sensitivity analyses, in addition to the statistical test described in this table.
	

Table 38: According-to-Protocol Analysis of DOOR at D5V - ATP-5 Analysis Population

Statistic	Value
Subjects with all DOOR components measured – n (%)	x (x)
Subjects with one or more DOOR components imputed – n (%)	x (x)
Pr(Higher DOOR in Placebo Arm) ^a (95% CI) ^a	x.xx (x.xx, x.xx)
P-value ^b	x.xxx
^a Probability of Higher DOOR in Placebo Arm at D11V + 0.5 Probability of Equal DOOR. 95% CI obtained through inversion of the F-test used to compute the p-value. ^b P-value obtained by Mann-Whitney U Test. P-value boundary of 0.05 is used to conclude statistical significance. It is important to note that conclusions from DOOR analyses must rely on a detailed assessment of the DOOR components as well as consideration of sensitivity analyses, in addition to the statistical test described in this table.	

Table 39: Deterioration in LRTI Symptoms at D5V - ATP-5 Analysis Population

Symptom	Azithromycin				Placebo				Difference (95% CI) ^b	P-Value ^c
	N	n	%	95% CI ^a	N	n	%	95% CI ^a		
Any Symptom	x	x	x	(x.x, x.x)	x	x	x	(x.x, x.x)	xx (x.x, x.x)	x.xxx
Cough	x	x	x	(x.x, x.x)	x	x	x	(x.x, x.x)	xx (x.x, x.x)	x.xxx
Sputum Production	x	x	x	(x.x, x.x)	x	x	x	(x.x, x.x)	xx (x.x, x.x)	x.xxx
Chest Pain	x	x	x	(x.x, x.x)	x	x	x	(x.x, x.x)	xx (x.x, x.x)	x.xxx
Difficulty Breathing	x	x	x	(x.x, x.x)	x	x	x	(x.x, x.x)	xx (x.x, x.x)	x.xxx

N = Number of subjects in the ATP-5 analysis population and the respective treatment group having the symptom at baseline with non-missing severity.

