n = Number of subjects with at-least one step deterioration (worsening from mild to moderate for example) in any qualifying symptom regardless whether the symptom was present at enrollment or not.
^a95% CI for proportions calculated using the Wilson method.
^b95% CI for the difference in proportions, placebo relative to azithromycin, calculated using the Miettinen–Nurminen method.
^cP-values obtained by Fisher’s Exact Test.

Table with similar format:

Table 40: Deterioration in LRTI Symptoms at D11V - ATP-11 Analysis Population

[Implementation Note: Update the footnote to use ATP-11.]

Table 41: Improvement in Symptom or Vital Sign - ATP-5 Analysis Population

Symptom	Azithromycin				Placebo				Difference (95% CI) ^b	P-Value ^c
	N	n	%	95% CI ^a	N	n	%	95% CI ^a		
Any Symptom or Sign	x	x	x	(x.x, x.x)	x	x	x	(x.x, x.x)	xx (x.x, x.x)	x.xxx
Any Symptom	x	x	x	(x.x, x.x)	x	x	x	(x.x, x.x)	xx (x.x, x.x)	x.xxx
Any Sign	x	x	x	(x.x, x.x)	x	x	x	(x.x, x.x)	xx (x.x, x.x)	x.xxx
At Least 2 Symptoms or Signs	x	x	x	(x.x, x.x)	x	x	x	(x.x, x.x)	xx (x.x, x.x)	x.xxx
Cough	x	x	x	(x.x, x.x)	x	x	x	(x.x, x.x)	xx (x.x, x.x)	x.xxx
Sputum Production	x	x	x	(x.x, x.x)	x	x	x	(x.x, x.x)	xx (x.x, x.x)	x.xxx
Chest Pain	x	x	x	(x.x, x.x)	x	x	x	(x.x, x.x)	xx (x.x, x.x)	x.xxx
Difficulty Breathing	x	x	x	(x.x, x.x)	x	x	x	(x.x, x.x)	xx (x.x, x.x)	x.xxx
Temperature	x	x	x	(x.x, x.x)	x	x	x	(x.x, x.x)	xx (x.x, x.x)	x.xxx
Pulse	x	x	x	(x.x, x.x)	x	x	x	(x.x, x.x)	xx (x.x, x.x)	x.xxx
Respiratory Rate	x	x	x	(x.x, x.x)	x	x	x	(x.x, x.x)	xx (x.x, x.x)	x.xxx

N = Number of subjects in the ATP-5 analysis population and the respective treatment group with the symptom or vital sign abnormality present at baseline.

n = Number of subjects with the vital sign abnormality at baseline whose symptom or vital sign improved.

^a95% CI for proportions calculated using the Wilson method.

^b95% CI for the difference in proportions, placebo relative to azithromycin, calculated using the Miettinen–Nurminen method.

^cP-values obtained by Fisher's Exact Test.

Table 42: New Occurrence of Vital Sign Abnormality or Presence of Fever at D5V - ATP-5 Analysis Population

Symptom	Azithromycin				Placebo				Difference (95% CI) ^b	P-Value ^d
	N	n	%	95% CI ^a	N	n	%	95% CI ^a		
Any Vital Sign	x	x	x	(x.x, x.x)	x	x	x	(x.x, x.x)	xx (x.x, x.x)	x.xxx
Temperature	x	x	x	(x.x, x.x)	x	x	x	(x.x, x.x)	xx (x.x, x.x)	x.xxx
Pulse	x	x	x	(x.x, x.x)	x	x	x	(x.x, x.x)	xx (x.x, x.x)	x.xxx

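### Tables 39 and 40: in the individual-symptom rows the deterioration count includes subjects outside its own denominator, and new symptoms at Day 11 have no analysis

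*SAP*

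**What the plan says.** Two adjacent footnotes to Table 39 (SAP Appendix 1, 14.2 Efficacy Data) define the display. The denominator is "N = Number of subjects in the ATP-5 analysis population and the respective treatment group having the symptom at baseline with non-missing severity". The numerator is subjects with at least a one-step deterioration "in any qualifying symptom regardless whether the symptom was present at enrollment or not". Table 40, "Deterioration in LRTI Symptoms at D11V - ATP-11 Analysis Population", uses the same format, and its only instruction is to change the population name in the footnote. The other footnotes specify Wilson intervals for each proportion, Miettinen–Nurminen intervals for the difference and Fisher's exact test.

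The body text is narrower. SAP 8.2.12 says that deterioration at Day 5 "will be analyzed in subjects having the symptom at baseline". SAP 8.3.7, under a Day 11 heading, says "at D5V compared to baseline will be analyzed in subjects having the symptom at baseline" and also names the ATP-5 population. Protocol 11.4.2 item 13 (Day 5) and Protocol 11.4.3 item 7 (Day 11) carry the same restriction to subjects with the symptom at baseline.

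New symptoms appear among the aims. Secondary objective 12 in Protocol 3.1 begins "To compare groups receiving azithromycin versus placebo in regard to new vital sign abnormalities or symptoms on Day 5". Exploratory outcome 6 (Protocol 3.2.3 and SAP 3.2.3) is, in its first part, the proportion of subjects with at least one new symptom on Day 11.

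**The concern.** A subject without chest pain at enrollment who has mild chest pain at Day 5 meets the definition of n in the chest pain row but is not in N. Wilson, Miettinen–Nurminen and Fisher all treat n as a count out of N. If n includes people outside N, the printed percentage is not a proportion of any group and the interval and p-value have no valid basis. Unless n exceeds N, the calculation still runs and gives no warning.

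Following the body text removes that fault but creates a gap. New symptoms then leave the four symptom rows, and no other SAP table reports them: Table 42 covers new vital sign abnormalities and fever at Day 5, and Table 45 covers fever at Day 11. SAP 2.1 says that every component of clinical improvement will be analyzed individually. The deterioration component in SAP 6.5.1.2 includes new symptoms, so rows restricted to baseline-positive subjects do not describe it fully.

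At stake is how symptom worsening without an antibiotic is reported by symptom, and whether the choice between two readings is made before or after the data are seen.

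**Working it through.** The documents give no figure for symptom deterioration, so there is nothing to reproduce. The check compares definitions and then sizes the mismatch under assumed rates.

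**Definitions side by side**

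- Table 39, individual rows: n includes new onset; N excludes subjects who could have new onset. They do not match.
- SAP 6.5.1.2 (composite endpoint): almost the same numerator wording, but every subject is assessed, so the rule is sound there. This is the likely source of the footnote.
- Table 42 (new vital sign abnormality): n and N are both confined to subjects without the abnormality at baseline. They match.
- Table 39, Any Symptom row: inclusion criterion 1 (Protocol 5.1) requires at least one qualifying symptom, so N is close to the whole ATP-5 population and nearly everyone counted in n is also in N.

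**Inputs**

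- 280 subjects per arm: Protocol section 5 and SAP 6.6 (560 evaluable in total).
- Baseline prevalence p, worsening rate d among those with the symptom, and onset rate e among those without it: assumed; none is in the documents.

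**Formulas**

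- As footnoted: [280pd + 280(1-p)e] / 280p = d + e(1-p)/p
- Restricted to subjects with the symptom at baseline: d
- All subjects: pd + (1-p)e

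The excess of the footnoted figure over the restricted one is e(1-p)/p. At e = 10%, it is 0.10 × 0.05/0.95 = 0.5 point at p = 95%, 0.10 × 0.20/0.80 = 2.5 points at p = 80%, and 0.10 × 0.60/0.40 = 15 points at p = 40%.

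**In whole subjects, with d = 10%**

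| p | e | N | worsened | new onset | as footnoted | restricted | all subjects |
|---|---|---|---|---|---|---|---|
| 95% | 10% | 266 | 27 | 1 | 28/266 = 10.5% | 27/266 = 10.2% | 28/280 = 10.0% |
| 80% | 10% | 224 | 22 | 6 | 28/224 = 12.5% | 22/224 = 9.8% | 28/280 = 10.0% |
| 40% | 10% | 112 | 11 | 17 | 28/112 = 25.0% | 11/112 = 9.8% | 28/280 = 10.0% |
| 20% | 20% | 56 | 6 | 45 | 51/56 = 91.1% | 6/56 = 10.7% | 51/280 = 18.2% |
| 10% | 20% | 28 | 3 | 50 | 53/28 = 189% | 3/28 = 10.7% | 53/280 = 18.9% |

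Counts are rounded to whole subjects, so the differences depart slightly from the formula.

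**Effect on an arm comparison**

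Take p = 40% and 11 of 112 worsening in both arms, with onset among the other 168 of 5% on azithromycin (8 subjects) and 15% on placebo (25 subjects).

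- As footnoted: 36/112 − 19/112 = 17/112 = 15.2 points.
- Restricted: 11/112 − 11/112 = 0.
- All subjects: 36/280 − 19/280 = 17/280 = 6.1 points.
- New onset among those at risk: 25/168 − 8/168 = 17/168 = 10.1 points.

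The footnoted difference matches none of the three valid estimates. The restricted one shows nothing, although onset differs between the arms.

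**The case against.** The strongest reply is that the plan already contains a valid rule. Two SAP sections and the protocol agree on subjects with the symptom at baseline. A program that subsets to those subjects before counting keeps n within N, and all three methods are then valid. The numerator footnote looks carried over from SAP 6.5.1.2, and nearby shells have similar slips: the footnotes to Tables 37 and 38, which are Day 5 tables, refer to Day 11. This stands as far as it goes. A reader might infer that the deterioration results are bound to be wrong, but the documents do not show that; the error arises only if the shell is programmed as footnoted. The reply does not remove the contradiction, and it leaves new symptoms without rows of their own.

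A reader might also infer that secondary objective 12 goes unanswered. At Day 5 that is too strong. Outcome measure 12 expresses the objective as worsening in at least one symptom plus new vital sign abnormality and names no separate new-symptom proportion. The Any Symptom row as footnoted serves the first part, and Table 42 the second. The Day 5 gap is against the objective's wording only. The Day 11 gap is firmer, because exploratory outcome 6 names the proportion explicitly.

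Finally, a reader might infer that a central safety signal is lost. New symptoms already count as failure in the primary endpoint (SAP 6.5.1.2) and so enter the ordinal outcome and DOOR. Medically attended visits have Tables 43 and 44, and Listing 17 shows symptoms by subject and study day.

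**Conclusion.** The point holds for the four individual-symptom rows of Tables 39 and 40. Their numerator and denominator footnotes conflict with each other, and the numerator conflicts with SAP 8.2.12, SAP 8.3.7 and Protocol 11.4.2 item 13. Programmed as footnoted, those rows and their tests are invalid.

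The size cannot be fixed from the documents, since it depends on baseline prevalence and onset rates that they do not give. The distortion is trivial for a symptom almost everyone has at entry and large for an uncommon one; with d = 10% and p = 10%, any onset rate above 0.10 × 0.90/0.90 = 10% pushes the ratio past 100%.

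On the restricted reading the rows are valid, but exploratory outcome 6 has no analysis for its new-symptom part. These are secondary and exploratory ATP displays, and the primary non-inferiority analysis does not depend on them. The correction is worth making before final analysis because it is cheap and avoids a choice between readings made afterward.

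**What to change.** 1. In the individual-symptom rows of Tables 39 and 40, count n only among subjects with the symptom at baseline and drop the clause on symptoms absent at enrollment. This agrees with the protocol and SAP body text.
2. Add new-onset rows for each symptom at Day 5 and Day 11, with N = subjects without the symptom at baseline, as Table 42 does for vital signs.
3. Define the Any Symptom deterioration row over all subjects in the ATP population with non-missing severity at baseline and at the visit, and state whether new onset counts. Counting it would follow SAP 6.5.1.2.
4. Add an any-new-symptom row over the same subjects. At Day 11 this supplies the missing part of exploratory outcome 6.
5. Bring Figures 12 and 13 into line, and change the Day 5 and ATP-5 labels in SAP 8.3.7 to Day 11 and ATP-11.

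Widening N to all subjects in the symptom rows would give a valid proportion, but it would pool onset with worsening and depart from the population in Protocol 11.4.2 item 13, so it is not enough alone.

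The cost is a few table rows and revised derivation wording. Symptom severity is already collected, so no new data are needed.
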